5.1.2 Adverse Reaction (AR)

An AR is any untoward and unintended response in a participant during an experiment in which a causal relationship between the study intervention and an adverse event is a reasonable possibility.

5.1.3 Serious Adverse Event (SAE)

An SAE is any unfavourable medical occurrence that results in any of the following:

- Inpatient hospitalisation or prolongation of existing hospitalization
- A persistent or significant disability or incapacity
- A congenital anomaly or birth defect
- A life-threatening^a experience
- Death
- Important medical events that may be considered an SAE when - based on appropriate medical judgement - they may jeopardise the participant and may require medical or surgical intervention to prevent one of the above outcomes

^a The term "life threatening" in the definition of SAE refers to an event in which the participant was at risk of death at the time of the event. It does not refer to an event which hypothetically might have caused death if it was more severe.

5.1.4 Serious Adverse Reaction (SAR)

A SAR is an adverse reaction that meets the criteria for a serious adverse event (see 5.1.3 Serious Adverse Event).

5.1.5 Adverse Events of Special Interest (AESI)

The following events should be reported within the same timelines as SAEs:

- Adverse events related during iCPET
 - ECG signifying myocardial injury
 - ECG signifying current or potentially lethal arrhythmias
 - Systemic hypotension (e.g. systolic blood pressure < 90 mmHg)
 - Extreme hypertension (e.g. systolic blood pressure > 220 mmHg)
 - Syncope, presyncope, or lightheadedness
 - SaO₂ < 88%
 - Severely elevated PCWP (> 40 mmHg) during exercise
- Adverse events related to jugular catheter insertion and PCWP-measurement
 - Air embolism
 - Pulmonary artery perforation
 - Infection
 - Pneumothorax
 - Arrhythmias
 - Hypotension
- Adverse events related to arterial catheter insertion
 - Permanent vessel occlusion
 - Pseudoaneurysm formation
 - Infection
 - Air embolism

5.2 Adverse Events that do not require reporting

In general, the following should not be reported as AEs:

- Pre-existing conditions, including those found as a result of screening (these should be reported as medical history or concomitant illness). However, in case the pre-existing condition appears to be enhanced by the study intervention, this should be reported as an AE.
- Pre-planned procedures, unless the condition for which the procedure was planned has worsened from the first study-related activity after the participant has signed the informed consent.

The following events are commonly observed and are therefore not considered as adverse events for the purpose of the study:

- Delayed muscle onset pain
- Local pain at the site of cannulation
- Hematoma

Although these events should not be reported to the Sponsor, these should be recorded in the participant's medical notes according to routine practice.

The following events not to be considered as SAEs are:

- Pre-planned hospitalisations unless the condition for which the hospitalisation was planned has worsened from the first study-related activity after the participant has signed the informed consent.
- Hospitalisation as part of a standard procedure for protocol therapy administration. However, prolonged hospitalization or hospitalisation for a complication of therapy administration will be reported as an SAE.
- Hospitalisation or prolongation of hospitalisation for technical, practical, or social reasons, in absence of an AE.

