This study aims to assess the impact of accelerated pacing with tailored AV-regulation on the PCWP during exercise in patients with HFpEF, particularly at lower intensities of exertion, which are most relevant for daily activities. By determining whether accelerated pacing improves PCWP during exertion, we aim to provide insights into novel pacing-based interventions that could enhance exercise tolerance and ultimately improve quality of life in patients with HFpEF.

Risk assessment

When performed in experienced centers, right heart catheterization (RHC) is generally considered a safe procedure with low morbidity and mortality rates. A comprehensive analysis of 7,218 procedures, including both retrospective (5,727 cases) and prospective (1,491 cases) data, found an overall serious adverse event rate of 1.1% (95% CI: 0.8%–1.3%). The most frequent complications were related to venous access, such as hematoma and pneumothorax, followed by arrhythmias and hypotensive episodes due to vagal reactions or pulmonary vasoreactivity testing. The vast majority of these complications were mild to moderate in intensity and resolved spontaneously or with appropriate intervention (29). More severe complications are rare. Complete heart block or air embolism can lead to chest pain, shortness of breath, and hypotension. Pulmonary artery perforation, seen in approximately 0.03% of cases, may cause sudden respiratory distress and cardiogenic shock. In these cases, complications may require advanced medical intervention (30).

Radial artery canalization is generally well tolerated; complications are uncommon and include, but are not exclusive to, temporary or permanent vessel occlusion, pseudoaneurysm formation, infection, and, rarely, air embolism. Local pain at the site of cannulation, however, is common and may persist for days (31).

Potential complications of CPET include fatigue, leg pain and shortness of breath. Less common complications include cardiac arrhythmias, anginal chest pain, and bronchospasm. Additionally, CPET may lead to hypotension, occasional premature ventricular contractions (PVCs), and, in rare cases, significant ST-segment depression, which typically resolve after test termination. Overall, CPET remains a safe procedure with a low incidence of complications when conducted under medical supervision (32, 33).

2 Study objectives & design

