5.3.2 Study safety risks & mitigation measures

The risks associated with the study specific interventions are:

- **Blood collection:** Venous blood samples are taken in a procedure that is not different from taking blood for other purposes in standard clinical care. Although taking blood from the vein is a safe procedure, it may cause slight discomfort and result in mild bruising, swelling or redness. To minimize these risks, blood samples will be drawn by experienced health care providers using aseptic techniques and appropriate post-procedure care will be provided
- **Echocardiography:** Echocardiography is assessed in a procedure that is not different from doing a echocardiography for other purposes in standard clinical care. As a non-invasive imaging modality, echocardiography is considered a safe procedure with no known significant risks. Any potential discomfort due to prolonged probe contact will be minimized by ensuring appropriate patient positioning and communication during the procedure.
- **Invasive CPET:** iCPET involves:
 - **Right heart catheterization and PCWP-measurements** in a procedure that is not different for other purposes in standard clinical care. Although RHC is regarded as a safe procedure when performed in experienced centers, it may cause venous access-related issues (hematoma, pneumothorax) as well as arrhythmias and hypotension due to vagal reactions. Severe complications (air embolism or

pulmonary artery perforation) are rare. To mitigate the risk on complications, patients will undergo thorough medical evaluation excluding those with a history of unstable arrhythmias, severe tricuspid regurgitation or severe pulmonary hypertension, recurrent syncopes, or contra-indications for central venous access. Furthermore the procedure will be performed by an experienced interventional cardiologist, ultrasound guided and in sterile conditions, further limiting risks. An defibrillator will be available bedside in case of emergency.

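### The haematoma exemption in section 5.2 has no seriousness limit and conflicts with the serious-event rules, so a serious haematoma can go unreported

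*Combined protocol and SAP*

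**What the plan says.** Section 5.2 introduces a short list with "The following events are commonly observed and are therefore not considered as adverse events for the purpose of the study". The list has three items: delayed muscle pain, local pain where the cannula was placed, and haematoma. The last is a single unqualified word. The handling rule follows: "Although these events should not be reported to the Sponsor, these should be recorded in the participant's medical notes according to routine practice".

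The Risk assessment in section 1 says of right heart catheterisation: "The most frequent complications were related to venous access, such as hematoma and pneumothorax". Section 5.3.2 again pairs haematoma with pneumothorax as a venous-access risk. Section 5.1.5 sets out events of special interest on SAE timelines. Under the heading "Adverse events related to jugular catheter insertion and PCWP-measurement" it includes pneumothorax, arrhythmias and hypotension, and its arterial list includes pseudoaneurysm. Haematoma is in neither list.

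The general definitions carry no haematoma exception. Section 5.1.3 begins "An SAE is any unfavourable medical occurrence that results in any of the following", and section 5.1.4 says "A SAR is an adverse reaction that meets the criteria for a serious adverse event".

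**The concern.** The exemption works at the level of the definition: it says that haematoma is not an adverse event at all. An adverse reaction in 5.1.2 presupposes an adverse event, and a SAR in 5.1.4 presupposes an adverse reaction. The 24-hour duty in 5.3.4, the overview table in 5.4.2 and the annual report to the ethics committees are built on ARs, SARs, events of special interest and deaths. If haematoma drops out at the first step, a haematoma with a serious outcome need not enter that chain.

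At stake is whether the Sponsor, and through it the ethics committees, would learn of a serious access-site haematoma in a study that places a jugular and a radial catheter in each participant. There are two sites, and section 7.3 waives monitoring by anyone independent of the study team. Each site would therefore settle the conflict alone, and the only sentence that names haematoma tells it not to report.

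**Working it through.** This is a question of text. No stated figure depends on it, so there is none to reproduce.

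**Step 1. Is the exemption limited?** No. The other exclusions in 5.2 carry limits. Pre-existing conditions count as AEs if the intervention appears to aggravate them. Pre-planned procedures and pre-planned hospital stays count if the underlying condition has worsened. Hospital stays for giving protocol therapy count if they are prolonged or caused by a complication. The list containing haematoma has no such limit.

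**Step 2. Which sections point towards reporting a serious haematoma, and which away?**

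| Towards reporting | Away from reporting |
|---|---|
| 5.1.3: an SAE is any unfavourable occurrence with a serious outcome; not built on the AE definition | 5.2: haematoma is not an AE, with no limit |
| 5.2: its separate list of events that are not SAEs does not include haematoma | 5.2: "Although these events should not be reported to the Sponsor" |
| 5.2: hospitalisation for a complication of therapy administration is an SAE | 5.1.2 and 5.1.4: AR, and therefore SAR, presupposes an AE |
| 5.3.1: all events go in the medical record and the eCRF | 5.2: medical notes only |
| 5.3.4: causally related SAEs are reported; SARs within 24 hours | 5.4.2: the SAR row allows exceptions that the protocol defines, which can be read as pointing to 5.2 |
| 5.3.7: deaths are reported whatever the cause | 5.1.5: haematoma is not an event of special interest |

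**Step 3. Does any sentence rank the two columns?** None does. The hospitalisation sentence helps only if catheterisation counts as therapy administration, which the protocol does not say. The conflict with 5.3.1 also affects non-serious haematomas: one section sends them to the eCRF, the other to the notes only.

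**Step 4. Scale, for context only.** Inputs are the serious-event rate for right heart catheterisation in the Risk assessment (1.1%, 95% CI 0.8% to 1.3%, 7,218 procedures) and n = 20 from section 6.1. Expected events = n × p. Chance of at least one = 1 − (1 − p)^n.

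- p = 0.011: 20 × 0.011 = 0.22 expected; 1 − 0.989^20 = 0.198.
- p = 0.008: 20 × 0.008 = 0.16 expected; 1 − 0.992^20 = 0.148.
- p = 0.013: 20 × 0.013 = 0.26 expected; 1 − 0.987^20 = 0.230.

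These figures cover every kind of serious catheter event. The documents give no rate for haematoma, serious or otherwise.

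**The case against.** The strongest reply is that the protocol already captures a serious haematoma. The SAE definition does not rest on AE status. Haematoma is absent from the list of non-SAEs, and it sits beside two minor complaints, which suggests that only minor bruising was meant. Section 5.3.4 requires causally related SAEs to be reported, and deaths are always reported. Pseudoaneurysm and hypotension are events of special interest, so some consequences of a serious bleed are reportable anyway. A bleed that is not a haematoma is not exempt.

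Much of this stands. A reader might infer from 5.2 that every serious access-site bleed escapes reporting and that nothing else would pick it up. The documents do not support that: one fair reading of 5.1.3, 5.2 and 5.3.4 captures a serious haematoma, 5.3.1 sends all events to the eCRF, and 7.1.1.1 links prompt eCRF entry to the Sponsor's safety reviews. The reply does not resolve the conflict, however. It shows that a second reading exists, and no sentence says that it governs.

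A reader might also take the 20% as the chance of a missed serious haematoma. It is not. The 1.1% includes pneumothorax, arrhythmia and hypotension, which are reportable here as events of special interest. The Risk assessment says that the vast majority of complications were mild to moderate. By its title, the cited series is in patients with pulmonary hypertension, whereas section 3.2 excludes severe pulmonary hypertension.

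Finally, the annual report lists SARs only, so non-serious haematomas would be absent from that overview even without the exemption. What matters there is the serious case, which should be rare.

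**Conclusion.** The point holds as an unresolved contradiction. Section 5.2 removes haematoma from AE status and from Sponsor reporting without a seriousness limit, while 5.1.3, 5.3.1 and 5.3.4 require serious, related events to be recorded and reported. A site that applies 5.2 literally could leave a serious haematoma unreported. A site that applies 5.1.3 and 5.3.4 would report it. The documents do not establish that such events would be missed as a rule.

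The size cannot be calculated from the documents. The 19.8% chance of at least one serious catheter event of any kind (14.8% to 23.0%) is a ceiling for serious haematoma from the venous catheter. It assumes that the cited rate carries over to this population and that participants are independent. It says nothing about the radial site, for which no rate is given. The primary and secondary analyses are unaffected. The consequence is for safety oversight, and the correction is cheap enough to be worth making.

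**What to change.** Reconcile 5.2 with 5.1.3, 5.3.1 and 5.3.4. Add to 5.2 that the exemption covers only haematoma meeting none of the seriousness criteria in 5.1.3, and that any haematoma meeting one is recorded and reported under the existing SAE and SAR rules and timelines. The same clause should say whether exempt, non-serious haematomas still go in the eCRF under 5.3.1 or only in the medical notes.

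Routine bruising stays exempt, so the aim of avoiding trivial reports is kept. No new criteria, timeline or procedure is needed. The cost is one clause and at most a few extra forms across 20 participants.

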5.3 Recording & reporting of Adverse Events

5.3.1 AE recording

Investigators will seek information on AEs during each participant contact. All events, whether reported by the participant or noted by study staff, will be recorded in the participant's medical record and in the eCRF within a reasonable time after becoming aware. The diagnosis rather than the individual signs or symptoms should be reported, if available. If no diagnosis is available, the Investigator should record each sign and symptom as individual AEs.

The following minimum information should be recorded for each (S)AR:

- AE description
- Start and stop date of the AE
- Severity
- Seriousness
- Causality assessment to the study interventions
- Outcome

5.3.2 Study safety risks & mitigation measures

The risks associated with the study specific interventions are:

- **Blood collection:** Venous blood samples are taken in a procedure that is not different from taking blood for other purposes in standard clinical care. Although taking blood from the vein is a safe procedure, it may cause slight discomfort and result in mild bruising, swelling or redness. To minimize these risks, blood samples will be drawn by experienced health care providers using aseptic techniques and appropriate post-procedure care will be provided
- **Echocardiography:** Echocardiography is assessed in a procedure that is not different from doing a echocardiography for other purposes in standard clinical care. As a non-invasive imaging modality, echocardiography is considered a safe procedure with no known significant risks. Any potential discomfort due to prolonged probe contact will be minimized by ensuring appropriate patient positioning and communication during the procedure.
- **Invasive CPET:** iCPET involves:
 - **Right heart catheterization and PCWP-measurements** in a procedure that is not different for other purposes in standard clinical care. Although RHC is regarded as a safe procedure when performed in experienced centers, it may cause venous access-related issues (hematoma, pneumothorax) as well as arrhythmias and hypotension due to vagal reactions. Severe complications (air embolism or

pulmonary artery perforation) are rare. To mitigate the risk on complications, patients will undergo thorough medical evaluation excluding those with a history of unstable arrhythmias, severe tricuspid regurgitation or severe pulmonary hypertension, recurrent syncopes, or contra-indications for central venous access. Furthermore the procedure will be performed by an experienced interventional cardiologist, ultrasound guided and in sterile conditions, further limiting risks. An defibrillator will be available bedside in case of emergency.

- **Radial artery cannulation** in a procedure that is not different for other purposes in standard clinical care. Placement of an radial artery cannula can cause slight discomfort and result in mild bruising, swelling or redness. Local anaesthesia will be used. While complication such as temporary or permanent vessel occlusion, pseudoaneurysm formation, infection, and, rarely, air embolism can occur, these events are uncommon. All risks will be limited due to the availability of an experienced interventional cardiologist, performing the cannulation in sterile conditions. An Allen test will be performed at study inclusion to make sure there is adequate collateral circulation through the ulnar artery, ensuring hand perfusion in case of radial artery occlusion. Patients will undergo thorough medical evaluation excluding those with contraindications for radial artery cannulation.

Access sites will be monitored throughout the whole procedure. Both cannulas will be removed in sterile conditions. Hemostasis will be ensured by applying manual pressure or a hemostatic device as per standard protocol.

- **CPET** on a semi supine cycle ergometer in a procedure that is not different for other purposes in standard clinical care. CPET is a widely used diagnostic tool that is considered safe when conducted under medical supervision. However, potential complications can occur. Common symptoms include fatigue, leg pain, and shortness of breath. Less frequently, cardiac arrhythmias, anginal chest pain, and bronchospasm may develop. Rare complications include hypotension, occasional premature ventricular contractions (PVCs), and significant ST-segment depression, which typically resolve once the test is terminated. To mitigate the risk on complications, patients will undergo thorough medical evaluation excluding those with unstable coronary syndrome, decompensated heart failure, history of unstable arrhythmias, severe pulmonary hypertension and aortic stenosis. Throughout the procedure, a physician will monitor the participant to ensure safety and promptly manage any adverse events. An defibrillator will be available bedside in case of emergency.

- **Accelerated pacing with the pacemaker ON/OFF procedure:**

- During the study protocol, pacemaker settings will be actively adjusted to alternate between intrinsic rhythm (back-up pacing mode) and accelerated pacing at various frequencies. Previous studies involving stepwise increases in pacing rates in patients with HFpEF have all been conducted safely (26, 36-39). Nevertheless, accelerated pacing may pose certain physiological risks, including a reduction in diastolic filling time, potentially leading to diastolic underfilling and subsequent blunting of the Frank-Starling mechanism. These changes may contribute to hypotension and orthostatic symptoms (40). Pacing frequency will be limited to the age-predicted maximum heart rate (APMHR), preventing supraphysiological rates in patients with elevated resting heart rates. Furthermore, abrupt transitions between pacing OFF and ON settings may cause palpitations, dyspnoea, or

dizziness. To avoid excessive heart rate fluctuations, the backup pacing rate during OFF episodes in exercise will be increased to approximately 20 bpm below the intrinsic heart rate at that level of exertion, rather than reverting to the resting backup mode. To mitigate potential risks, only patients in stable sinus rhythm will be included. All pacemaker adjustments will be performed under supervision of a cardiologist. Transitions between pacing modes will occur gradually, with continuous ECG and hemodynamic monitoring throughout. The study will take place in a fully equipped medical environment with a defibrillator and trained staff present at all times. In case of any signs of hemodynamic compromise, pacing will be immediately restored to a safe backup mode.

5.3.3 Assessment

All AEs must be evaluated by an Investigator as to:

- **Seriousness:** whether the AE is an SAE. See above for the seriousness criteria.
- **Severity:**

Severity must be evaluated by an Investigator according to the following definitions:

- *Mild* – no or transient symptoms, no interference with the participant's daily activities
- *Moderate* – marked symptoms, moderate interference with the participant's daily activities
- *Severe* – considerable interference with the participant's daily activities, unacceptable

- **Causality:**
 - *None* – An AE which is not related to the study related interventions.
 - *Unlikely* – An AE for which an alternative explanation is more likely (e.g. concomitant medication(s), concomitant disease(s)), and/or the relationship in time suggests that a causal relationship is unlikely.
 - *Possible* – An AE which might be due to the study related interventions. An alternative explanation is inconclusive. The relationship in time is reasonable; therefore the causal relationship cannot be ruled out.
 - *Probable* – An AE which might be due to study related interventions. The relationship in time is suggestive (e.g. confirmed by dechallenge). An alternative explanation is less likely.
 - *Definitely* – An AE which is listed as a possible adverse reaction and cannot be reasonably explained by an alternative explanation. The relationship in time is very suggestive (e.g. it is confirmed by dechallenge and rechallenge).

